### **2.6. Inclusion Criteria**

- Patients aged  $\geq 1$  months and  $< 19$  years
- Patients diagnosed with Primary Immunodeficiency Diseases eligible for an allogeneic transplantation and lacking a related HLA-matched donor
- Lansky/Karnofsky score  $> 40$ , WHO  $> 4$
- Signed written informed consent

### **2.7 Exclusion Criteria**

- Dysfunction of liver (ALT/AST  $> 5$  times normal value, or bilirubin  $> 3$  times normal value), or of renal function (creatinine clearance  $< 30$  mL / min)

### **2.8 Therapeutic plan**

Conditioning regimen:

Drug	Total dose	Days
Treosulfan	42g/m  (36g/m  for patients under 1 year of age)	-5, -4, -3
Fludarabine	150mg/m 	-6, -5, -4, -3, -2
ATGAM	90mg/kg	-5, -4

Post-transplant GVHD prophylaxis – calcineurin inhibitors based in combination with methotrexate 5 mg/m^2 on days +1, +3, and +6 or MMF - mycophenolate mofetil 30 mg/kg till day +60 post-HSCT.

### **3. Methods**

#### ***3.1 Graft processing***

Hematopoietic stem cell grafts will be derived from the granulocyte colony-stimulating factor -mobilized peripheral blood mononuclear cell fraction. Depletion of TCR alpha beta T cells and B cells (CD19) will be performed with CliniMACS Plus instrument (Miltenyi Biotec, Bergisch Gladbach, Germany). After depletion procedure, the numbers of nucleated cells CD34+, CD3+ and CD3+TCRab+ will be estimated in final product.

#### ***3.2 GVHD, Viral infections and Serious adverse events***

Acute and chronic GVHD will be diagnosed and graded using standard guidelines (10). For cytomegalovirus (CMV) and Epstein-Barr virus (EBV) detection in blood and other biologic liquids quantitative real-time polymerase chain reaction (PCR) analysis will be used. CMV and EBV levels will be routinely monitored weekly until CD41 T-cell recovery was above  $0.3 \times 10^9/L$ . CMV disease will be identified with the detection of CMV in affected tissue. To grade the severity of serious adverse events, the National Cancer Institute Common Terminology Criteria for Adverse Events (CTCAE) will be used.

#### ***3.3 Engraftment, Chimerism and Graft Failure***

Neutrophil engraftment will be registered on the first day of an absolute neutrophil count above  $0.5 \times 10^9/L$ , platelet engraftment on the first of 5 subsequent days of platelet counts more than  $50 \times 10^9/L$  without platelet transfusions, as well as by full donor chimerism at day +30.

Graft failure includes all cases of non-engraftment and graft rejection after demonstrated engraftment with the detection of more than 90% of the patient's chimerism in peripheral blood or bone marrow.

Whole peripheral blood and CD3+ lineage chimerism assessments will be performed monthly until day + 180 and then performed once every 3 months until day + 360. For chimerism testing in-house, a reverse transcriptase PCR system for the detection of short

tandem repeat markers will be used. To demonstrate graft failure additional analysis of bone marrow CD34+ cells will be assessed.

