### **2.3 Secondary purposes**

- to evaluate overall and event-free survival (at 2 years post-HSCT)
- to estimate the risks of serious adverse events (at 1 year post-HSCT)
- to evaluate the rate of primary engraftment and risks of graft failure (at 2 years post-HSCT)
- to estimate risks and severity of acute and chronic graft versus host disease (at 1 and 2 years post-HSCT, respectively)
- to estimate risks of viral infections (at 1 year post-HSCT)
- to evaluate transplant related mortality (at 2 years post-HSCT)
- to estimate a kinetics of immune recovery (at 2 years post-HSCT)
- to estimate levels of donor chimerism (at last follow up)

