### **2.4. Primary endpoint**

1. Overall survival (OS) 2 years after HSCT, defined as time from transplantation to death of any cause

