### **2.5. Secondary endpoints**

2. Cumulative incidence of transplant-related mortality 1 year after HSCT
3. Cumulative incidence and severity of acute GVHD II-IV grade 1 year after HSCT

4. Cumulative incidence of chronic GVHD 2 years after HSCT
5. Number of participants, who reached immune recovery (CD3+, CD19+ lymphocytes subsets and intravenous immunoglobulin independence) 2 years after HSCT
6. Percentage of patients with full (more than 90%) donor chimerism among survivals at last follow-up
7. Cumulative incidence of CMV reactivation 1 year after HSCT

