### ***3.5 Statistical analysis***

The patients will be censored at the time of death or at the last FU in survivors (the minimum FU period in survivors was 0,5 years).

The probability of overall and event free survival (OS and EFS) will be estimated by the Kaplan-Meier method. For EFS analysis as events will be considered graft failure, deaths, severe graft dysfunctions due to mixed chimerism, severe organ damage due to HSCT complications. The probabilities of acute and chronic GVHD, graft failure, viral reactivations and transplant-related mortality will be estimated with cumulative incidence curves (considering competitive risks, e.g., graft failure or death).

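### Section 3.3 registers neutrophil engraftment on one day's count, with no sustained-count or post-nadir condition, so the engraftment date, and possibly the status, can be wrong

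*Combined protocol and SAP*

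**What the plan says.** One sentence in section 3.3 of the combined protocol and SAP carries three elements.

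- Neutrophils: "Neutrophil engraftment will be registered on the first day of an absolute neutrophil count above" 0.5 × 10⁹/L.
- Platelets: "platelet engraftment on the first of 5 subsequent days of platelet counts more than" 50 × 10⁹/L.
- The closing clause: "without platelet transfusions, as well as by full donor chimerism at day +30".

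The meaning of full chimerism appears only in section 2.5, for a different time point: "Percentage of patients with full (more than 90%) donor chimerism among survivals at last follow-up".

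Engraftment status is then used in several places. Section 3.3 continues: "Graft failure includes all cases of non-engraftment and graft rejection after demonstrated engraftment", with a threshold of more than 90% recipient chimerism. Section 2.3 lists as a secondary purpose "to evaluate the rate of primary engraftment and risks of graft failure (at 2 years post-HSCT". Section 3.5 says "For EFS analysis as events will be considered graft failure, deaths, severe graft dysfunctions due to mixed chimerism", and it also gives graft failure its own cumulative incidence curve. The primary endpoint in section 2.4 is overall survival, "defined as time from transplantation to death of any cause".

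**The concern.** An engraftment definition should separate recovery of the graft from two other things: residual recipient neutrophils that have not yet fallen after conditioning, and a brief rise that is not maintained. The neutrophil rule does neither. The authors wrote a persistence condition for platelets in the same sentence, so its absence for neutrophils stands out. No other section supplies one.

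Three results are at stake: the day on which engraftment is recorded, possibly the proportion recorded as engrafted, and the division of graft failures into those that never engrafted and those that engrafted and were later rejected. The Background names graft failure among the most serious complications of haploidentical transplantation, so that division has clinical meaning for readers of the trial.

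**Working it through.** There is no stated figure to reproduce. The documents give no engraftment rate, sample size or blood-count schedule, so the check is a reading of the text.

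**Step 1. Compare the two count rules in section 3.3.**

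| Condition | Neutrophils | Platelets |
|---|---|---|
| Threshold | 0.5 × 10⁹/L | 50 × 10⁹/L |
| Days required | 1 | 5 |
| Guard against an artificial value | none | no transfusions |
| Must follow the nadir | not stated | not stated |
| Day from which counting starts | not stated | not stated |

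**Step 2. Can a pre-nadir count satisfy the rule?** Section 2.8 places conditioning on days -6 to -2. Taking day 0 as the day of infusion, the last listed conditioning drug is given 0 - (-2) = 2 days before it. The documents do not say that neutrophils are already below 0.5 × 10⁹/L by then, and the rule does not require them to have been. A count that is still above the threshold shortly after infusion meets the rule as written. So does a single later rise that is not maintained.

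**Step 3. What does the day +30 chimerism clause change?** The linking words allow three readings.

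| Reading of the clause | Engraftment date | Engraftment status |
|---|---|---|
| Required jointly with the counts | exposed | protected for patients with a day +30 result |
| A separate criterion | exposed | exposed |
| Applies to platelets only | exposed | exposed |

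The date is exposed on every reading, because chimerism at day +30 confirms whether the graft took but does not move the registered day. Status is exposed on two of the three.

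**Step 4. Deaths before day +30.** Such a patient has no day +30 result. Under the joint reading the text does not say whether the patient counts as engrafted on the blood count alone, as not engrafted (and so a graft failure), or as not evaluable.

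**Step 5. Follow a misregistered patient through graft failure and event-free survival (EFS).** Take a patient who never truly engrafted but had one qualifying count.

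- Classified correctly: non-engraftment, which is graft failure and an EFS event.
- Misregistered, then shown to have more than 90% recipient chimerism: rejection after engraftment, which is also graft failure and an EFS event.
- Misregistered, then dies: death, which is an EFS event.

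On these paths an EFS event is recorded. What can change is its date and its label. In the separate graft-failure curve, the last path could move a patient from graft failure to the competing event of death.

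**Step 6. Primary endpoint.** Overall survival depends only on the date of transplantation and death from any cause. Engraftment does not enter it.

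**The case against.** The strongest reply is that the sentence does not end with the counts. If full donor chimerism at day +30 is required together with them, a residual recipient count or an isolated rise without donor chimerism is not engraftment. Section 3.3 adds further checks on graft failure: monthly chimerism testing to day +180, and marrow CD34+ analysis to demonstrate failure. This has real force for status, but only under one reading of ambiguous wording, and it leaves the recorded date unprotected.

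A second reply is that reach is limited. Engraftment is not among the endpoints listed in section 2.5, and section 3.5 names no analysis of engraftment rate or time to engraftment. That is true, and it keeps this a point about secondary measures. It does not remove the point, because the rate of primary engraftment is a stated purpose in section 2.3 and non-engraftment is part of the graft-failure definition.

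A reader might also infer more than the text supports:

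- *That the engraftment rate will be overstated.* The documents show only that it is open to overstatement, and only if chimerism is not a joint requirement.
- *That the number of EFS events changes.* Non-engraftment, rejection and death are all EFS events under sections 3.3 and 3.5, so relabelling a patient does not remove the event.
- *That a false-registration percentage can be given.* This would need a daily chance of an isolated rise, the dependence between days, the length of aplasia and the proportion who never engraft. The documents give none of these.

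**Conclusion.** The point holds in a limited form. As written, the neutrophil rule can record the engraftment date too early on any reading of section 3.3. It can also record the wrong status if day +30 chimerism is not a joint condition. The consequences fall on time to engraftment, the rate of primary engraftment, and the split between non-engraftment and later rejection. EFS is affected at most in when an event is dated, and 2-year overall survival not at all.

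The size cannot be calculated from the documents. The conclusion rests on taking the sentence literally, and on the assumption that some patients have a neutrophil count above the threshold before the nadir or for one day only. The documents neither confirm nor exclude this. If the site already applies a persistence rule in practice, the defect is one of text alone, but the text is what a later analyst will follow.

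**What to change.** Amend section 3.3 in two respects.

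1. Define neutrophil engraftment as the first of a stated number of consecutive days (for example 3) with a count above 0.5 × 10⁹/L after the post-conditioning nadir. Both parts are needed: a run of days alone could be met before the nadir, and a nadir condition alone could be met by an isolated rise. The choice of 3 is an example and does not come from the documents. The platelet rule uses 5.
2. State whether engraftment status also requires full donor chimerism at day +30. Confirm that the threshold of more than 90% from section 2.5 applies there, and say how patients who die before day +30 are classified.

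The change alters an endpoint definition and not treatment. It costs a sentence or two. The reported engraftment rate and time may look slightly less favourable. It also needs serial neutrophil counts: the documents give no blood-count schedule, though the 5-day platelet rule already implies serial counts. The sponsor should confirm that neutrophil counts are available at the spacing that the chosen rule needs.

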### ***3.4 Immune reconstitution***

For immune recovery kinetics in whole blood will be analysed monthly until day + 180 and then once every 3 months until day + 360 routinely. Patients with no demonstrated immune recovery at 1 year after HSCT will be monitored via individual protocols. Lymphocyte subsets analysis will be performed via flow cytometry. Routinely monitored cell lines include: CD3+, CD19+, CD3-CD16+CD56+, CD3+CD16+CD56+, CD3+TCRalpha/beta+, CD3+TCRgamma/delta+, CD3+CD45RA+CD197+.

### ***3.5 Statistical analysis***

The patients will be censored at the time of death or at the last FU in survivors (the minimum FU period in survivors was 0,5 years).

The probability of overall and event free survival (OS and EFS) will be estimated by the Kaplan-Meier method. For EFS analysis as events will be considered graft failure, deaths, severe graft dysfunctions due to mixed chimerism, severe organ damage due to HSCT complications. The probabilities of acute and chronic GVHD, graft failure, viral reactivations and transplant-related mortality will be estimated with cumulative incidence curves (considering competitive risks, e.g., graft failure or death).

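### The only censoring rule in section 3.5 censors patients at death, although section 2.4 makes death the event for overall survival, the primary endpoint

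*Combined protocol and SAP*

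**What the plan says.** Section 2.4 gives the primary endpoint as "Overall survival (OS) 2 years after HSCT, defined as time from transplantation to death of any cause". Death is the event.

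Section 3.5 begins with the rule "The patients will be censored at the time of death or at the last FU in survivors", followed in parentheses by "the minimum FU period in survivors was 0,5 years". It names no endpoint, and the document contains no other censoring rule.

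The rest of section 3.5 deals with estimation:

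- For OS and EFS: "The probability of overall and event free survival (OS and EFS) will be estimated by the Kaplan-Meier method".
- For EFS events: "For EFS analysis as events will be considered graft failure, deaths, severe graft dysfunctions due to mixed chimerism", with severe organ damage from transplant complications as a further event.
- For the cumulative incidence analyses, which include transplant-related mortality: "considering competitive risks, e.g., graft failure or death".

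Section 3.5 lists events for EFS but not for OS. The event for OS comes only from the endpoint definition in section 2.4.

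**The concern.** In a time-to-event analysis, censoring has a fixed meaning: the patient's event time is known only to lie beyond the last observation. A patient who dies has an observed OS time. Coding that patient as censored at death discards the outcome that the endpoint measures.

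The rule applies to patients in general and sits directly before the sentence naming the OS estimator. A programmer working from section 3.5 alone would find an instruction to censor deaths and nothing in that section to exempt OS. At stake is the coding of the primary endpoint. The statistical section is only two short paragraphs, so there is no fuller specification to fall back on.

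**Working it through.** The plan states no OS figure, sample size, expected mortality or maximum follow-up, so there is no planned figure to reproduce. The check compares the text and then follows the literal rule through the estimator.

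**Step 1. How each analysis treats death.**

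| Analysis | Treatment of death in its own text | Under the opening rule of 3.5, read literally |
|---|---|---|
| OS (primary) | Event (2.4) | Censored |
| EFS | Event (3.5) | Censored |
| Cumulative incidences | Competing risk (3.5) | Censored |

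The opening rule disagrees with the specific text in every row. For EFS and the cumulative incidences, section 3.5 itself settles the matter. For OS, the correction has to be brought in from section 2.4.

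**Step 2. The literal rule applied to OS.** The Kaplan-Meier estimate at 2 years is

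S(2) = product over event times t_j ≤ 2 of (1 − d_j / n_j),

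where d_j is the number of events at t_j and n_j the number at risk. The only OS event is death. If every death is censored, no event time exists and the product has no factor below 1. So S(2) = 1, or 100%. Greenwood's variance, S(2)² × Σ d_j / [n_j (n_j − d_j)], has no terms, so the standard error is 0. This holds for any data set and needs no simulation.

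**Step 3. Size of the gap under the literal reading.** The gap is 100% minus the OS estimate with death as the event. The plan gives no expected OS, so the values below are assumptions that show the range only:

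| Assumed 2-year OS | Literal estimate | Gap |
|---|---|---|
| 70% | 100% | 100 − 70 = 30 points |
| 80% | 100% | 100 − 80 = 20 points |
| 90% | 100% | 100 − 90 = 10 points |
| 95% | 100% | 100 − 95 = 5 points |

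The gap is just the assumed 2-year mortality. It says nothing about what the trial will report.

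**Step 4. What the sentence probably means.** It pairs death with last follow-up in survivors, and its parenthesis concerns length of follow-up. Both fit a description of when observation stops. Under that reading a death ends observation as an event, a survivor's time ends as a censoring, and sections 2.4 and 3.5 agree.

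**The case against.** The strongest objection is that the plan already settles the matter for OS as well. Section 2.4 is as specific for OS as the EFS event list is for EFS, and a specific definition should override a loosely worded general sentence. A Kaplan-Meier estimate of OS has no purpose if no patient can have an event. No coherent reading of the whole document codes deaths as OS censorings, and an experienced analyst would not do so.

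Most of this stands. It establishes the intent and keeps the point minor. It does not make the sentence right: the only censoring rule in the plan still says the opposite of the primary endpoint definition, and the reader must override it to compute that endpoint. The sentence is complete and current, so neither redaction nor superseded text explains it.

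A reader might infer two stronger points, and the documents support neither:

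- **OS will be reported as 100%, or inflated by some number of points.** This would require the literal rule to be followed against section 2.4 and the rest of section 3.5. The gaps in the working describe the literal reading and are not expected bias.
- **The EFS, transplant-related mortality and other cumulative incidence estimates are left undefined or biased.** The opening rule does clash with that text, but the event list and the competing-risk sentence already say how death is handled there. No figure is claimed for those endpoints.

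**Conclusion.** The censoring rule in section 3.5 is wrong as written and conflicts with the primary endpoint definition in section 2.4. The point is minor. Taken literally, the rule gives an OS estimate of 100% in any data set, a result that rests on algebra alone and on no assumed sample size, mortality or follow-up. The judgement that this is a wording error rests on reading sections 2.4 and 3.5 together, and they agree that death is meant to count. The rule should be corrected, but no effect on the trial's results is predicted.

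**What to change.** Replace the opening sentence of section 3.5 with wording such as:

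> Observation ends at death or at last follow-up. Only patients alive without the event of interest or a competing event are censored, at last follow-up (minimum follow-up in survivors: 0.5 years). Death from any cause is the event for OS and an event for EFS, and is never a censoring.

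Two things should be preserved. The parenthesis is the document's only statement of minimum follow-up, so it must be carried over. The sentence naming graft failure or death as competing risks should stay unchanged: a new list of competing events that named death alone would leave the role of graft failure unclear.

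The cost is one rewritten sentence. It needs no further data, patients or analyses.

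### The 2-year immune-recovery count has no estimator, denominator or rule for survivors followed for less than 2 years, while the only stated minimum follow-up is 0.5 years; for 2-year OS the cost is precision, not bias

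*Combined protocol and SAP*

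**What the plan says.** The primary endpoint in section 2.4 is "Overall survival (OS) 2 years after HSCT". Section 2.3 also places event-free survival and immune-recovery kinetics at 2 years, and section 2.5 places chronic GVHD there.

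The fifth endpoint in section 2.5 is "Number of participants, who reached immune recovery", with a 2-year horizon. It names no denominator. The next endpoint is limited to survivors ("donor chimerism among survivals at last follow-up"); the recovery endpoint is not.

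Section 3.5 assigns Kaplan-Meier to OS and EFS, and cumulative incidence curves to GVHD, graft failure, viral reactivation and transplant-related mortality. It names no method for immune recovery. For survivors it censors at last follow-up, adding that "the minimum FU period in survivors was 0,5 years". That clause is the only minimum patient follow-up in the visible sections. The schedules to day +360 in sections 3.3 and 3.4 are laboratory assessments. Section 3.4 adds: "Patients with no demonstrated immune recovery at 1 year after HSCT will be monitored via individual protocols". No visible section gives an accrual period, an analysis trigger or a data cut-off.

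**The concern.** A 2-year result normally rests on patients who have been followed for 2 years, or on a method that handles those who have not. The plan has such a method for OS, EFS and chronic GVHD, but not for immune recovery. A survivor last seen at 6 months and not yet recovered has an unknown 2-year outcome. A plain count has no place for an unknown outcome, so whoever does the analysis must decide how to treat that patient. The most natural default, not recovered, pushes the result down. Section 3.4 keeps unrecovered patients under observation after 1 year, so later recoveries can be seen if the analysis waits for them or censors properly.

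For the survival-type endpoints, the question is how many patients are still under observation at 2 years when the analysis is run. Nothing visible guarantees that this number is adequate.

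**Working it through.** The plan states no sample size, expected OS, accrual length or recovery rate, so there is no figure of its own to reproduce. What follows is illustration.

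**Inputs from the documents:** a 2-year horizon (sections 2.4 and 2.5) and minimum follow-up m = 0.5 years (section 3.5).

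**Assumed:** uniform accrual over A = 2, 3 or 5 years; data cut-off m years after the last transplant; no other loss; n = 50; 2-year OS 85%; 2-year recovery in 80% of all transplanted patients.

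**1. Share with at least 2 years' potential follow-up** = max(0, (A + m − 2)/A).
- A = 1.5: 0/1.5 = 0%. For A below 1.5, nobody can be observed to 2 years.
- A = 2: 0.5/2 = 25%. A = 3: 1.5/3 = 50%. A = 5: 3.5/5 = 70%.

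**2. Immune recovery under three counting rules that the text allows.** Let F(t) be the cumulative incidence of recovery, with F(2) = 0.80. The slow curve has a constant rate (F(1) = 0.55). The fast curve has 90% of the 2-year recoveries by 1 year (F(1) = 0.72).

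- Rule a: recoveries seen so far count, everyone else is a failure, and all patients are in the denominator. Proportion = [∫ F(t) dt from 0.5 to 2]/A + 0.80 × (A − 1.5)/A. The integral is 0.918 (slow) or 1.097 (fast). At A = 2, slow: 0.918/2 + 0.80 × 0.25 = 0.659.
- Rule b: only patients who have reached 2 years can count as recovered, and all patients are in the denominator. Proportion = 0.80 × share from step 1.
- Rule c: only patients with at least 2 years' potential follow-up are in numerator and denominator. Proportion = 0.80.

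| A (years) | Rule a, slow to fast | Rule b | Rule c |
|---|---|---|---|
| 2 | 66-75% | 20% | 80% |
| 3 | 71-77% | 40% | 80% |
| 5 | 74-78% | 56% | 80% |

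The sample size n appears in none of these formulas, so more patients do not remove the error.

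**3. Precision of 2-year OS.** With complete follow-up, half-width = 1.96 × √(0.85 × 0.15/50) = 9.9 points. With staggered follow-up, the Greenwood variance is multiplied by R = [∫ h/(S·G) dt]/[∫ h/S dt] over 0 to 2 years. Here h is the hazard, S the survival function, and G(t) = 1 up to m and (A + m − t)/A after it. Two hazard shapes are used: 80% of the cumulative hazard in the first 6 months (early), and constant.

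| A (years) | R, early / constant | Half-width = 9.9 × √R | Expected at risk at 2 years = 50 × 0.85 × share |
|---|---|---|---|
| 2 | 1.182 / 1.668 | 10.8-12.8 | 10.6 |
| 3 | 1.083 / 1.303 | 10.3-11.3 | 21.2 |
| 5 | 1.041 / 1.148 | 10.1-10.6 | 29.7 |

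Complete follow-up would leave 50 × 0.85 = 42.5 at risk. At A = 2 the chance of fewer than 10 at risk is about 36% (binomial, n = 50, probability 0.85 × 0.25 = 0.2125). With m = 1 and A = 2, R is 1.055 / 1.204 and the half-width 10.2-10.9.

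For scale, complete follow-up gives 12.8 points at n = 30 and 7.0 at n = 100. At 3 years' accrual or more, the sample size therefore matters more to precision than the follow-up does.

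**The case against.** Several objections carry weight.

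- *OS is handled correctly.* Kaplan-Meier is valid under administrative censoring. A reader might infer that a 0.5-year minimum makes the 2-year OS estimate biased or invalid; the documents do not support that. At 3 years' accrual the loss is 0.4-1.4 points of half-width, and at 5 years 0.2-0.7. This stands, and for OS the point is conditional on short accrual.
- *The 0.5 years may be an observed minimum.* The clause is in the past tense, and section 3.5 is missing from the table of contents, which hints at text added later. This is not decisive, because section 3.2 also mixes tenses. If the minimum is observed, it may reflect one recently transplanted survivor, and the figures above would not apply. A reader might infer that the sponsor plans to analyse 6 months after the last transplant; the text does not establish that.
- *The recovery shortfall depends on a counting rule that the plan does not state.* This also stands. The documents support calling the endpoint undefined; they do not support any particular shortfall. The spread between rules a, b and c shows how much is left open.
- *Other durations and dates may exist.* The day +360 schedules do exist, but they govern laboratory tests. Some front pages were not available for review, so an accrual period or cut-off stated there cannot be excluded. Dates alone would still not supply an estimator or denominator for recovery.

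**Conclusion.** The point holds as a gap in definition for immune recovery and as a conditional loss of precision for the survival-type endpoints.

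For immune recovery, a raw 2-year count combined with survivors followed for as little as 0.5 years can give too low a result. That happens if those not yet at 2 years are treated as not recovered, and sample size does not cure it. Its size in this trial cannot be given from the visible sections.

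For OS, EFS and chronic GVHD there is no bias, provided follow-up ends for reasons unrelated to outcome. The loss is small with accrual of 3 years or more or mainly early deaths. It is serious if accrual is about 1.5 years or less, when few or no patients reach the horizon. All OS figures rest on assumed n, survival, hazard shape and uniform accrual, with the analysis run at the stated minimum. They illustrate the mechanism and are not evidence about this trial. The change is worth making because it is cheap; confidence is medium.

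**What to change.** 1. Analyse immune recovery as the cumulative incidence of first documented recovery by 2 years over all transplanted patients, with death as a competing event and survivors censored at last follow-up. This handles lost survivors and patients who recover and later die, which a simple proportion does not. It should not be restricted to 2-year survivors.
2. Report the number at risk at 2 years and the median follow-up beside every 2-year estimate.
3. State whether 0.5 years is planned or observed, and replace the clause with a pre-stated cut-off for the primary analysis. The preferred cut-off is 24 months' follow-up from transplantation in every survivor not documented as lost to follow-up. A lighter option is at least 12 months in every survivor plus a pre-stated minimum number at risk at 2 years. Label any earlier analysis interim.

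**Cost.** Items 1 and 2 need a little more analysis work and no delay. If 0.5 years was the planned minimum, item 3 moves the lock by up to 24 − 6 = 18 months, or 12 − 6 = 6 months with the lighter option; if it was observed, the delay may be shorter. No extra patients are needed. Item 1 reads the endpoint as recovery reached by 2 years. If the sponsor means status at 2 years, measurements at that time would be needed in patients who recovered earlier, and the routine schedule in section 3.4 does not provide them.
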